5.11.4 PROBABLE: (MUST HAVE THREE OUT OF FOUR CRITERIA)

This category applies to those adverse experiences which, after careful medical consideration at the time they are evaluated, are felt with a high degree of certainty to be related to the study drug. An adverse experience may be considered likely related if or when:

- The adverse experience follows a reasonable temporal sequence from the time of drug administration.
- The adverse experience follows a known response pattern to the study drug.
- The adverse experience cannot be reasonably explained by other factors such as the patient's clinical state, therapeutic interventions, or concomitant drugs administered to the patient.
- The adverse experience is confirmed by improvement of the symptoms on de-challenge (e.g., the removal withdrawal, or discontinuation of the suspected drug from the patient's therapeutic regimen).

5.11.5 DEFINITE: (MUST HAVE ALL FOUR CRITERIA)

This category applies to those adverse experiences that the Investigator feels are incontrovertibly related to the study drug. An adverse experience may be assigned an attribution of definitely related if or when:

- The adverse experience follows a reasonable temporal sequence from the time of drug administration.
- The adverse experience cannot be reasonably explained by the known characteristics of the patient's state, environmental or toxic factors, or other modes of therapy administered to the patient.
- The adverse experience occurs immediately following study drug administration, or improves on stopping the drug (de-challenge), or reappears on repeat exposure (re-challenge) (Note: this is not to be construed as requiring re-exposure of the patient, however, a category of definitely related can only be used when recurrence is observed).
- The adverse experience follows a known response pattern to the study drug.

5.11.6 ASSESSMENT OF THE SEVERITY OF ADVERSE EVENTS

Severity of an adverse experience is defined as a qualitative assessment of the degree of intensity of an adverse experience as determined by the Investigator or reported to him/her by the patient. The assessment of severity is made irrespective of drug relationship or seriousness of the event using MEDRA criteria.

All serious and life threatening adverse experiences must be reported by entering them into the database and no later than 24 hours after the Investigator has become aware of them. This will generate automatic emails to the study Sponsor and the study monitors. The patient must be monitored carefully until the condition disappears and/or the etiology is defined.

All serious and life threatening adverse experiences must be reported by the Investigator to the appropriate IRB/EC in writing, as well as the study sponsor.

5.12 Recording of Concomitant Therapy

All prescription and nonprescription medication (including vitamins and herbal supplements) taken by the patient from screening to the end of the study will be recorded in the patient's medical record and the eCRF. Any additions, deletions or changes in the dose of these medications should be entered on this form. Generic names should be used to eliminate confusion that may result from trade names. The list of all concomitant medications will be reviewed at each visit, and adjusted as appropriate.

5.13 Study Discontinuation Criteria

The occurrence of a grade 3 or 4 AE in any patient will result in the immediate discontinuation from this study. In the event of a grade 2 AE, the Investigator, at their discretion, may withhold treatment until the event resolves to grade 1 or less.

The Sponsor may at its discretion terminate the study as a whole if conditions warrant this action. The study site Investigator bears responsibility for orderly discontinuation of the study subjects enrolled at his/her study site.

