5.2 Drug Administration

5.2.1 THE L1-79 REGIMEN

Subjects will receive either 100 mg or 200 mg or matching placebo t.i.d. for a total of 28 days of dosing. The doses of L1-79 were determined based upon preliminary clinical research in subjects between 2½ and 24 years of age and doses between 90 and 200 mg t.i.d..

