5.14 Dose Adjustment and Stopping Rules

As this is a double-blind trial and the doses administered to a given patient are not known to the Investigator or the sponsor. In the event a grade 1 or 2 adverse event occurs, the regimen will be paused until a resolution of the event occurs and the Investigator feels it is safe to continue. Should the Investigator feel it is not safe to continue, or should the event reoccur that patient will be terminated from this trial and appropriate therapeutic measures taken. Any dosing hiatus or discontinuation will be noted in the case report form.

In the event a patient experiences a grade 3 (Severe) or 4 (Life Threatening) adverse event medication will be discontinued immediately and will not resume until the Investigator and the DMC have agreed that it is safe to do so.

In the event of two grade 3 (Severe) or 4 (Life Threatening) adverse events as found in the schedule of adverse events presented in [Appendix A](#), the study at any site will be stopped until such time as the Principal Investigator, Co-Investigator at that site and the Sponsor have determined appropriate measures to assure the safety of future subjects.

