APPENDIX A: STUDY PLAN ACTIVE TREATMENT PHASE

Form #	Form Name	Screening	wk 0 Baseline	Visit					
				Wk 1	Wk 2	Wk 3	Wk 4	1 wk post dosing	4 wk FUP
	Study Day		0 ± 2	7 ± 2	14 ± 2	21 ± 2	28 ± 2	35 ± 2	56 ± 2
1	Date of Visit	x	x	x	x	x	x	x	x
2	Informed Consent & Study Compliance agreement	x							
3	Demography	x							
4	Additional Patient Information	x							
5	Inclusion Criteria	x							
6	Exclusion Criteria	x							
7	Eligibility Criteria	x							
8	Medical history	x							
9	Family History	x							
10	Lab - Hematology (all patients)	x					x		x
11	Lab- Serum Chemistry (all patients)	x					x		x
12	Urine Analysis (all patients)	x					x		x
13	Lab - Hematology (Assigned patients only)		x*	x	x	x	x	x**	x
14	Lab- Serum Chemistry (Assigned patients only)		x*	x	x	x	x	x**	x
15	Urine Analysis (Assigned patients only)		x*	x	x	x	x	x**	x
16	PK/PD		x*	x	x	x	x		
17	Blood Draw	x					x	x**	x
18	Vital Signs - screening	x							
19	Vital Signs		x	x	x	x	x	x**	x
20	Physical Examination	x						x**	x
21	Randomization		x						
22	ADOS	x					x		
23	EKG (Assigned patients only)		x	x	x	x	x	x**	x
24	ADI-R (Telephonic)	x							
25	SAS		x					x**	x
26	VABS II		x				x	x**	x
27	ABC-C (all scales)		x	x	x	x	x	x**	x
28	SRS		x	x	x	x	x	x**	x
29	RBS-R		x	x	x	x	x	x**	x
30	CGI-S		x	x	x	x	x	x**	x
31	CGI-I			x	x	x	x	x**	x
32	CGI-Overall score		x	x	x	x	x	x**	x
33	Study Drug dispensing	x		x					
34	Study Drug Administration			x	x	x	x		
35	Drug Accountability				x		x		
36	Adverse Event		x	x	x	x	x	x**	x
37	Prior and Concomitant Medication	x	x	x	x	x	x	x**	x

*At baseline visit for Assigned Group Patients PK samples are to be taken before, and 1 hour after, the 1st dose. ** Assigned Group Patients Only

This schedule describes the study events for each patient on each study day where action is required.

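### Sections 5.13 and 5.14 give incompatible instructions after grade 3/4 and grade 2 adverse events, and the two-event site stop relies on an event list that Appendix A does not contain

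*Combined protocol and SAP*

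**What the plan says.** **Grade 3 or 4.** Section 5.13 ends the patient's participation: "The occurrence of a grade 3 or 4 AE in any patient will result in the immediate discontinuation from this study". Section 5.14 says that "medication will be discontinued immediately and will not resume until the Investigator and the DMC have agreed that it is safe to do so".

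**Grade 2.** Section 5.13: "In the event of a grade 2 AE, the Investigator, at their discretion, may withhold treatment until the event resolves to grade 1 or less". Section 5.14, covering grades 1 and 2 together: "In the event a grade 1 or 2 adverse event occurs, the regimen will be paused until a resolution of the event occurs".

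**Site stop.** Section 5.14 halts a site after two grade 3 or 4 events, until the site's investigators and the sponsor have settled what protection future patients need. It qualifies those events with the words "as found in the schedule of adverse events presented in" Appendix A. Appendix A describes itself differently: "This schedule describes the study events for each patient on each study day where action is required".

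Neither section refers to the other. Section 5.10, which lists reasons for discontinuing a patient, sets no order between them.

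**The concern.** Safety is the primary endpoint (3.2.1), the patients are males aged 13 to 21, and these are the rules for taking a patient off drug or halting a site. The planned treatment duration is the same for everyone: "Subjects will receive either 100 mg or 200 mg or matching placebo t.i.d. for a total of 28 days of dosing". How much of it a patient receives after an adverse event depends on the hold and restart rules. If two sites read different sections, the same event can lead to restart at one and removal at the other, or to continued dosing at one and a pause at the other. Exposure and discontinuation counts would then partly reflect which section a site followed. A site-stop rule whose qualifying events are not defined can be applied too narrowly or disputed at the moment it is needed.

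**Working it through.** There is no stated figure to reproduce, and no sample size, error rate or power enters. The check sets the two sections side by side and follows the cross-reference.

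**Step 1: compare the actions by event.**

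| Event | 5.13 | 5.14 | Can a site obey both? |
|---|---|---|---|
| New grade 3 or 4 | Patient leaves the study at once | Drug stopped at once; restart possible if Investigator and DMC agree | Only if the restart clause is never used |
| New grade 2 | Hold optional; after a hold, restart at grade 1 or lower | Hold required until the event resolves | Yes, by following 5.14; no, if the latitude in 5.13 is used |
| New grade 1 | No action stated | Hold required until the event resolves | No direct conflict; 5.14 is the only rule |
| Recurrent grade 1 or 2 | No action stated | Participation ends | No direct conflict; 5.14 is the only rule |

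*Grade 3/4.* A patient who has been discontinued from the study has no study drug to resume. The restart clause presupposes a patient who is still in the study, so each use of it contradicts 5.13. In the text available, the DMC it relies on is named only in that sentence.

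*Grade 2.* The sections differ on two things: whether a hold is required, and when it ends. A site that keeps dosing, or restarts when the event has fallen to grade 1, acts within 5.13 and breaches 5.14. A site that pauses until resolution breaches neither.

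**Step 2: look for a precedence rule.** Sections 5.10, 5.13 and 5.14 contain none.

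**Step 3: follow the Appendix A reference.** Appendix A lists forms 1 to 37 against visits. One of the 37 rows (form 36) concerns adverse events, and it shows only the visits at which they are recorded. Event types listed: 0. Grades defined: 0. By the table of contents, the other appendices are the rollover study plan (B), consent (C), compliance agreement (D), sample collection (E) and DSM-5 criteria (F), so the list has not simply been placed under another letter. Appendix A is present in the public text, so page removal does not explain the gap.

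**Step 4: what the trigger could mean.** Either any two recorded grade 3 or 4 events count, or only those on a narrower list that was left out. Under the second reading a site cannot work out whether the rule has been met.

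**The case against.** **Taking the stricter action satisfies both sections.** This is correct. Section 5.14 permits restart after grade 3/4 without requiring it, and pausing at grade 2 is one way of using the discretion in 5.13. But no text tells sites to do so, and reading the protocol that way leaves the restart clause and the grade 2 discretion with no effect. Sites may reasonably assume that both were written to be used.

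**The Appendix A reference is a slip.** This is plausible. Section 5.5 calls Appendix A the schedule of events, and other appendix letters are misplaced: 4.1 sends the reader to B for consent, which is in C, and 5.9.3.1 sends the reader to D for sample methods, which are in E. On that view any two grade 3 or 4 events count. The wording still restricts a safety trigger to a list that is absent, so the slip needs correcting.

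**Other safeguards exist.** They do: 24-hour reporting of serious events with automatic alerts (5.11.6, 8.1), monitoring of serious and life-threatening events until they disappear or are explained (5.11.6), Investigator discretion (5.10), sponsor termination (5.13, 8.7) and FDA review of first-week 100 mg data before escalation (5.1.1). Holds and discontinuations must also be noted on the case report form. These limit the harm and make differing exposure visible. None says which grade rule applies or which events count.

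**A stronger inference about grade 1.** A reader might infer a conflict at grade 1 as well, because 5.13 accepts grade 1 as the restart level after a grade 2 hold. The documents do not support that: 5.13 sets no action for a new grade 1 event. The same goes for recurrence, where 5.14 says "Should the Investigator feel it is not safe to continue, or should the event reoccur that patient will be terminated from this trial" and 5.13 is silent. Nor can a number of lost doses be attributed to the conflict, since the documents give no event rates or durations.

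**Conclusion.** The point holds, in two parts.

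1. The sections are incompatible on restart after a grade 3/4 event. At grade 2 they differ on the duty to hold and on the restart threshold. At grade 2 the incompatibility runs one way: following 5.14 satisfies both sections, and using the latitude in 5.13 does not.
2. The events that count toward the two-event site stop are not defined, because the list they are tied to is not in Appendix A.

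The size is bounded. A reader might infer that a patient could be kept on drug through a severe event; the documents do not support this, since both sections stop drug immediately at grade 3/4. A reader might also infer that trial conclusions are at risk. Section 6.1 plans descriptive statistics only, so no test result depends on the conflict. What is left open is who restarts, how consistently sites hold drug at grade 2, and when a site is stopped. This should be fixed, but it does not undermine the design.

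The conclusion assumes that the first sentence of 5.13 refers to the patient rather than to the whole study, which is how it reads, and that Appendix A appears in full in the public text.

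**What to change.** Delete the grade-action sentences from 5.13, leaving its paragraph on sponsor termination, and keep one rule per grade in 5.14:

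- **Grade 3 or 4:** permanent discontinuation of study drug, with safety follow-up continued. Delete the DMC restart clause.
- **Grade 2:** pause until resolution, as 5.14 already states.
- **Site stop:** delete the qualifier "as found in the schedule of adverse events presented in" Appendix A, so that any two grade 3 or 4 events trigger the stop. If the sponsor did intend a narrower list, insert it instead.

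The cost is about one page of amendment, with no added patients and no new visit types. There are trade-offs. A patient whose grade 3 or 4 event proves unrelated loses the route back to drug, though 5.13 already removes it. Investigators lose the grade 2 discretion in 5.13, which 5.14 already overrides. Counting any two grade 3 or 4 events may pause a site for unrelated events; inserting the intended list, if one exists, would avoid that.

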5.14 Dose Adjustment and Stopping Rules

As this is a double-blind trial and the doses administered to a given patient are not known to the Investigator or the sponsor. In the event a grade 1 or 2 adverse event occurs, the regimen will be paused until a resolution of the event occurs and the Investigator feels it is safe to continue. Should the Investigator feel it is not safe to continue, or should the event reoccur that patient will be terminated from this trial and appropriate therapeutic measures taken. Any dosing hiatus or discontinuation will be noted in the case report form.

In the event a patient experiences a grade 3 (Severe) or 4 (Life Threatening) adverse event medication will be discontinued immediately and will not resume until the Investigator and the DMC have agreed that it is safe to do so.

In the event of two grade 3 (Severe) or 4 (Life Threatening) adverse events as found in the schedule of adverse events presented in [Appendix A](#), the study at any site will be stopped until such time as the Principal Investigator, Co-Investigator at that site and the Sponsor have determined appropriate measures to assure the safety of future subjects.

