5.1.4 PLACEBO ROLLOVER TO ACTIVE

- If the Investigator in collaboration with Yamo Pharmaceuticals (the manufacturer of the drug) believes that the L1-79 is sufficiently well tolerated and clinically useful to warrant continued treatment, then patients receiving placebo will be eligible for a 4 week course of treatment with L1-79 as outlined for the other patients treated with active drug in this protocol. At the present time, the permitted course of therapy does not extend past 4 weeks.
- The random code will only be broken after the last patient in a group has completed the last scheduled follow-up visit.
- Placebo treated patients who qualify for active treatment in a rollover fashion, and who desire to do so, will be indicated in the eCRF as having affirmatively requested active treatment under the protocol. They will then qualify for extended treatment with active medication under the existing protocol and new, active, medication will be assigned to them on an open label basis at the same dose as their group had been receiving.
- Placebo rollover patients will be seen at 3 scheduled visits plus a follow-up visit as described in [Appendix B](#).
 - There will be no Screening, as patients have already been screened
 - Rollover patients will not have any PK tests conducted
 - Baseline Visit
 - No randomization is required.
 - Roll over patients will get a physical (including vital signs)
 - Blood and urine samples will be taken for hematology, urinalysis and serum chemistry assessments.
 - No retained samples to be collected
 - All psychometric assessments described in [Appendix A](#) for the baseline visit will be taken
 - The initial 2 weeks of doses of active medication will be dispensed.
 - Week 2
 - A physical examination will be performed and the parents interviewed as to their observations regarding the effects of treatment over the past two weeks, and the final two weeks of active medication doses will be dispensed.
 - Patients will get a physical (including vital signs)

- No blood or urine samples will be taken
- No psychometric tests will be conducted at this visit.
- Week 4
 - The final active treatment assessment will be made, which will include a physical examination,
 - All blood and urine analysis described previously
 - No retained samples to be collected
 - All psychometric tests described for the 4 week visit in [Appendix A](#).
 - Patients will get a physical (including vital signs)
 - A week 4 ADOS will be taken

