7.3 Dispensing the Study Drug

Study drug will be dispensed as a two week supply during study weeks 0 and 2 visits.. Drugs will be allocated to subjects on a randomized and double-blinded basis. Two containers of 42 doses will consist of the study drug for each patient. Each container will be labeled with the patient's study number.

At the accession visit prior to week 1 and at the post week 2 visit each patient will receive a container of drug corresponding to their study number. Neither the Investigator or the sponsor will know to which dosage group any patient is assigned.

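### Section 5.14 lets blinded parties restart the study after two grade 3 or 4 events without the DMC, and its trigger cites an adverse event list that Appendix A does not contain

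*Combined protocol and SAP*

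**What the plan says.** Section 5.14 sets two rules for grade 3 or 4 adverse events.

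- **One patient.** Medication stops at once and "will not resume until the Investigator and the DMC have agreed that it is safe to do so".
- **Two events.** "the study at any site will be stopped until such time as the Principal Investigator, Co-Investigator at that site and the Sponsor have determined" how to protect future subjects. The events that count are those "as found in the schedule of adverse events presented in" Appendix A.

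The same section says that "the doses administered to a given patient are not known to the Investigator or the sponsor". Section 7.3 repeats this: "Neither the Investigator or the sponsor will know to which dosage group any patient is assigned". Section 5.1.4 adds: "The random code will only be broken after the last patient in a group has completed the last scheduled follow-up visit". The exceptions are unblinding of an individual patient in an emergency or for an adverse event (sections 5.1.5 and 5.10) and the open-label Groups 1 and 3 (section 5.1.2).

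Appendix A describes itself thus: "This schedule describes the study events for each patient on each study day where action is required". Its only entry on the subject is a form row for adverse events.

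Section 5.13 has a rule of its own: "The occurrence of a grade 3 or 4 AE in any patient will result in the immediate discontinuation from this study".

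**The concern.** Safety is the primary endpoint (section 3.2.1). A second severe event is the stronger signal, yet the clause that governs restart names no independent body, while the clause for one patient does. The restart is left to people who, for the randomized groups, are not meant to know the arm. That makes it hard for them to judge whether the events point to the drug.

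The trigger is also hard to apply. It depends on a list that is not there, so sites could differ on which events qualify. It does not say whether the two events are pooled across sites. If the count is per site, one severe event at each of two sites would not force a stop.

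**Working it through.** The protocol gives no operating characteristics for this rule, so there is no figure to reproduce. The main point rests on the text; the arithmetic is illustration.

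**1. Who decides what.**

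| Situation | Who must agree | Knowledge of arm |
|---|---|---|
| One patient resumes (5.14) | Investigator and DMC | Investigator blinded; DMC access not described |
| Restart after two events (5.14) | Principal Investigator, site Co-Investigator, Sponsor | Blinded for randomized patients |

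Section 5.14 is the only place in the supplied text that mentions a DMC. Blinding covers Groups 2, 4 and 5: 10 + 10 + 10 = 30 patients. Groups 1 and 3 (5 + 5 = 10) have known doses.

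**2. The trigger.** Appendix A lists forms by visit, with no adverse event terms and no grades. Section 5.11.6 refers severity to MedDRA criteria, and section 5.14 attaches the labels severe and life threatening to grades 3 and 4. No numbered grading scale is set out. Nothing states whether events are counted per site or study-wide. Read literally, two events in one patient meet the trigger.

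**3. How much the counting unit matters.** The total of 40 patients is from the synopsis. Site number, site size and event rate p are assumed, because the documents give none. At most one event per patient is counted.

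- Study-wide: 1 − P(Bin(40, p) ≤ 1)
- Two sites of 20: 1 − P(Bin(20, p) ≤ 1)²
- Four sites of 10: 1 − P(Bin(10, p) ≤ 1)⁴

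| p | Study-wide | Two sites | Four sites |
|---|---|---|---|
| 0.01 | 0.061 | 0.033 | 0.017 |
| 0.02 | 0.190 | 0.116 | 0.063 |
| 0.05 | 0.601 | 0.459 | 0.303 |
| 0.10 | 0.920 | 0.847 | 0.706 |
| 0.20 | 0.999 | 0.995 | 0.980 |

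The gap between the first two columns is P(Bin(20, p) = 1)², the chance of exactly one event at each of two sites. It peaks at p = 1/20, where it is 0.142, and is about 0.07 at both p = 0.02 and p = 0.10.

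**4. What blinded parties cannot tell apart.** Take one cohort's 15 randomized patients (10 active, 5 placebo). Suppose two of them have an event and treatment has no effect on risk. There are C(15,2) = 105 pairs:

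- both active: C(10,2)/105 = 45/105 = 43%
- one of each: 10 × 5/105 = 50/105 = 48%
- both placebo: C(5,2)/105 = 10/105 = 10%

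Across all 40 patients at equal risk, both affected patients are randomized in C(30,2)/C(40,2) = 435/780 = 56% of cases. In the other 44% at least one dose is openly known.

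**The case against.** **The comparison with one patient may be empty.** Section 5.13 takes a patient with a grade 3 or 4 event off study. If it governs, nobody resumes and the DMC step in section 5.14 never operates. A reader might infer that resuming one patient in practice gets more independent review than restarting the study; the documents do not establish that. If section 5.14 governs instead, its rules add up, and the DMC would still be consulted on each affected patient for whom resumption is sought. The gap is then the resumption of everyone else. This narrows the contrast, but under either reading the restart clause does not name the DMC.

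**Other oversight exists.** A reader might infer that no independent body hears of these events. That is not so. Serious events go to the IRB in writing (sections 5.11.6 and 8.1), and unanticipated problems are reported to it promptly (section 8.3.3). FDA reviews first-week data from the five open-label 100 mg patients before escalation (sections 4.3 and 5.1.1). It also receives a second report on the open-label patients (section 5.1.2) and the 200 mg lead-in data (section 3.1). The Sponsor may terminate at its discretion (sections 5.13 and 8.7). All this stands, but none of it is a gate on restart. The 24-hour alert covers serious events and goes to the Sponsor and monitors, so a non-serious grade 3 event can fall outside it.

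**The blinding is not total.** Ten patients are open label, and section 5.1.4 may allow an earlier group's code to be opened while a later group is dosing. This limits the argument to the randomized patients whose code is still closed.

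**The probabilities prove little.** A reader might infer that severe events spread over sites will escape the rule. A study-wide count is a fair reading of the text, and under it the gap is zero.

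**The DMC is not described.** Its membership, remit and access to the code are not in the supplied text, and a charter may exist. This bears on the cost of the change rather than on the defect.

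**Conclusion.** The concern holds in a limited form. After two grade 3 or 4 events, section 5.14 leaves restart to parties who are blinded to arm for the 30 randomized patients and does not require the DMC's agreement. The trigger relies on an adverse event list that Appendix A does not contain. Both points rest on the text and hold however the two events are counted. They should be corrected.

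The size cannot be stated as a measure of harm. The only quantified effect is that of the counting unit: 46% against 60% at an assumed 5% rate with two assumed sites of 20, and 30% against 60% with four sites of 10. Both assume at most one event per patient, and both gaps vanish if the rule is already study-wide. These figures say nothing about what the DMC's absence costs.

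It would be tempting to restate the trigger as two affected patients. The text says two events, so that change would loosen the rule where both occur in one patient, and nothing in the documents supports it.

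**What to change.** Amend section 5.14 as follows.

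1. Require DMC agreement, with DMC access to events by arm and dose, before restart after the two-event stop. Report every grade 3 or 4 event from any site to the DMC.
2. Replace the reference to a list in Appendix A with any grade 3 or 4 adverse event, graded on one named scale.
3. Keep the trigger at two grade 3 or 4 events as written, including two in one patient, and state that they are counted across all sites.
4. Reconcile sections 5.13 and 5.14 on whether a patient with a grade 3 or 4 event may ever resume.

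**Cost.** The edits to section 5.14 are a few sentences. The DMC must be added to the existing 24-hour alert, with a short reporting rule for non-serious grade 3 events. The larger task is to write down the DMC's role, access to the code and turnaround time, which the supplied text does not describe. Confining the by-arm view to the DMC leaves the blind of the investigators and the Sponsor intact.

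If the rule was meant per site, stops become more likely, as the table shows, and each would interrupt 4-week courses. Events on placebo would count towards the stop until the DMC has reviewed them by arm.
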